3. STUDY OBJECTIVES AND ENDPOINTS

3.1. Research Hypothesis

INT230-6 when administered intratumorally (IT) to one or more tumors at an optimal dose to tumor volume ratio (i.e., greater than 1 mL per 4 cc of tumor) while treating a sufficient amount of the visible disease will safely reduce tumor burden, stabilize disease, promote an immune response against the cancer, and extend overall survival.

3.2. Objectives and Endpoints

Objectives and endpoints are described in [Table 2](#).

Table 2: Objectives and Endpoints

Cohort	Cohort Description	Number	Objective	Endpoint
A1	Dose Escalation, Monotherapy	PRIMARY	Safety and tolerability of multiple intratumoral doses of INT230-6 in subjects with advanced or recurrent malignancies	Grade 3, 4, or 5 study drug-related adverse events
B1				
EA				
EC				
EC2				

Cohort	Cohort Description	Number	Objective	Endpoint
		SECONDARY	
1) Assess the preliminary efficacy of INT230-6
 
2) Characterize the pharmacokinetic profile of multiple doses of the three INT230-6 components (CIS, VBL, and SHAO) after single and then multiple IT tumor site injections
 
3) Characterize the overall safety of the INT230-6
	
1) Disease Control Rate (CR+PR+SD) as defined by criteria based on RECIST 1.1
 
2) C_{max}, C_{min}, T_{max}, AUC_{TAU}, Accumulation index
 
3) Incidence and severity of treatment-emergent adverse events (TEAEs)
 
Clinical laboratory results (hematology, chemistry, urinalysis)
 
ECOG performance status
 
Physical examination, including vital sign measurements
 
ECG results

		EXPLORATORY	
1) Characterize tumor response in injected and non-injected sites
 
2) Evaluate various tumor and anti-tumor immune response biomarkers that may correlate with tumor response
 
3) Evaluate overall response by criteria based on RECIST or iRECIST
 
4) Characterize the pharmacodynamics (PD) profile of the INT230-6 formulation in subject blood and treated and untreated tumors
 
5) To assess the progression free (PFS) and overall survival (OS) in subjects receiving INT230-6 and cancer subtype of sarcoma.
	
1) Injected and Bystander tumor response rates to be conducted outside of this SAP.
 
2) Biomarker results
 
3) Response adjudicated as complete (CR), partial (PR), stable disease (SD), progressive disease (PD) or Not evaluable (NE); Best overall response and duration or response
 
4) PD profile results
 
5) PFS and OS as defined in Section 9.2 of this document

EC3	Highest set Dose, Monotherapy	PRIMARY SECONDARY EXPLORATORY	Objectives are the same as the above cohorts	

Cohort	Cohort Description	Number	Objective	Endpoint
DEC	Dose Escalation, Combination Therapy	PRIMARY	Assess the safety and tolerability of INT230-6 with pembrolizumab	Grade 3, 4, or 5 study drug-related adverse events attributed to the combination and not the underlying disease
		SECONDARY	1) Characterize the overall safety of INT230-6 combined with pembrolizumab 2) Assess the injected tumor response 3) Characterize the pharmacokinetic profile of multiple doses of the three INT230-6 components (CIS, VBL, and SHAO) after single and then multiple IT tumor site injections.	1) Incidence and severity of treatment-emergent adverse events (TEAEs) Clinical laboratory results (hematology, chemistry, urinalysis) ECOG performance status Physical examination, including vital sign measurements ECG results 2) Injected Response Rates 3) C_{\max} , C_{\min} , T_{\max} , AUC_{TAU} , Accumulation index
		EXPLORATORY	1) Characterize tumor response in injected and non-injected sites 2) Evaluate various tumor and anti-tumor immune response biomarkers that may correlate with tumor response 3) Characterize the pharmacodynamics (PD) profile of the INT230-6 plus pembrolizumab in subject blood and in treated and untreated tumors 4) Assess the overall survival in subjects receiving INT230-6 plus pembrolizumab meeting inclusion criteria.	1) Bystander Response Rates, Objective Response Rates, Best Overall Response, Duration of Response 2) Biomarker results 3) PD profile results 4) PFS and OS as defined in Section 9.2 of this document
DEC2	Highest INT230-6 Dose, Combination Therapy	PRIMARY	Preliminary efficacy of INT230-6 combined with pembrolizumab	Disease control rate (CR + PR + SD) of multiple intratumoral doses of INT230-6 combined with pembrolizumab and assessed with criteria based on RECIST or iRECIST
		SECONDARY	1) Characterize the overall safety of INT230-	1) Grade 3 or higher adverse events attributed to the

Cohort	Cohort Description	Number	Objective	Endpoint
			
6 combined with pembrolizumab
 
2) Assess the injected tumor response
 
3) Characterize the pharmacokinetic profile of multiple doses of the three INT230-6 components (CIS, VBL, and SHAO) after single and then multiple IT tumor site injections.
	
combination and not the underlying disease
 
Incidence and severity of treatment-emergent adverse events (TEAEs)
 
Clinical laboratory results (hematology, chemistry, urinalysis)
 
ECOG performance status
 
Physical examination, including vital sign measurements
 
ECG results
 
2) Injected Tumor Response Rate

	EXPLORATORY		
1) Characterize tumor response in injected and non-injected sites
 
2) Evaluate various tumor and anti-tumor immune response biomarkers that may correlate with tumor response
 
3) Evaluate overall response by criteria based on RECIST or iRECIST
 
4) Characterize the pharmacodynamics (PD) profile of the INT230-6 plus pembrolizumab in subject blood and in treated and untreated tumors
 
5) To assess the progression free and overall survival in subjects receiving INT230-6 plus pembrolizumab meeting inclusion criteria.
	
1) Injected and Bystander Response Rates; Objective response rates; Best overall response; Duration of Response
 
2) Biomarker results
 
3) Response adjudicated as complete (CR), partial (PR), stable disease (SD), progressive disease (PD) or Not evaluable (NE); Best overall response and duration or response
 
4) PD profile results
 
5) PFS and OS as defined in Section 9.2 of this document

FEC	Highest Dose, Combination Therapy	PRIMARY	Assess preliminary efficacy of multiple intratumoral doses of INT230-6 combined with the standard dose and schedule of Ipilimumab (3 mg/kg Q3 wk for 4 doses)	Disease control rate (CR + PR + SD) based on RECIST or iRECIST

Cohort	Cohort Description	Number	Objective	Endpoint
		SECONDARY	
1) Characterize the overall safety of the combination
 
2) Assess the preliminary efficacy of INT230-6 with Ipilimumab by measuring the injected and bystander tumor response
 
3) Characterize the pharmacokinetic profile of multiple doses of the three INT230-6 components cisplatin (CIS), vinblastine sulfate (VBL) and the cell penetration enhancer (SHAO) after single and then multiple IT tumor site injections
	
1) Grade 3 or higher adverse events attributed to the combination and not the underlying disease
 
Incidence and severity of treatment-emergent adverse events (TEAEs)
 
Clinical laboratory results (hematology, chemistry, urinalysis)
 
ECOG performance status
 
Physical examination, including vital sign measurements
 
ECG results
 
2) Injected and Bystander Response Rates
 
3) C_{max}, C_{min}, T_{max}, AUC_{TAU}, Accumulation index

		EXPLORATORY	
1) Characterize tumor response in injected and non-injected sites
 
2) Evaluate various tumor and anti-tumor immune response biomarkers that may correlate with tumor response
 
3) Evaluate overall response by criteria based on RECIST or iRECIST
 
4) Characterize the pharmacodynamics (PD) profile of the INT230-6 formulation in subject blood and treated and untreated tumors
 
5) To assess the progression free (PFS) and overall survival (OS) in subjects receiving INT230-6.
 
6) Explore the activity of the combination of INT230-6 with Ipilimumab compared to INT230-6 alone in patients with the same tumor types such as sarcoma.
	
1) Injected and Bystander tumor response rates
 
2) Biomarker results
 
3) Response adjudicated as complete (CR), partial (PR), stable disease (SD), progressive disease (PD) or Not evaluable (NE); Best overall response and duration or response
 
4) PD profile results
 
5) PFS and OS as defined in Section 9.2 of this document
 
6) Subgroup analysis of efficacy endpoints

4. STUDY DESIGN

4.1. General Study Design and Plan

This is a first-in-human (FIH) Phase 1/2, open label, non-randomized study. Subjects will have refractory, advanced cancers and will have failed at least 1 therapy or not be a candidate for standard of care. Investigators will have the option to continue INT230-6 based upon safety, local tolerability, and tumor response.

[Table 3](#) provides details on the Phase 1 cohorts included in this study. More details on dosing and injection can be found in the Study Protocol.

Table 3: Dosing for Phase 1 Cohorts

Study Part	Cohort	Tumor Type	Tumor Ratio (Dose)	Dosing Schedule	Combination Drug	Other
Escalation	A1	Superficial	1:4	Once per 28 days	No	Retreatment option after completing 5 doses
	B1	Superficial + Deep	1:4	Once per 28 days	No	
	EA	Superficial	1:4	Every 2 weeks	No	
	EC	Superficial and/or Deep	1:2	Every 2 weeks	No	
	EC2	Superficial and/or Deep	1:3	Every 2 weeks	No	
	DEC	Superficial and/or Deep	1:3	Every 2 weeks	Anti-PD1	
Phase 2/ Dose	EC3	Superficial and/or Deep	1:3 (Maximum 175 mL)	Every 2 weeks for 5 doses (Induction treatment)	No	Maintenance treatment every 9 weeks after completing 5 doses
	DEC2	Superficial and/or Deep	1:3 (Maximum 175 mL)	Every 2 weeks for 5 doses (Induction treatment)	Anti-PD1	
	FEC	Superficial and/or Deep	1:3 (Maximum 175 mL)	Every 2 weeks for 5 doses (Induction treatment)	Anti-CTLA4	

For purposes of analysis Cohorts A, B1, EA, EC are to be combined as one group as are cohorts EC2 and EC3. The A/B1,EA/EC population is defined as low loading monotherapy treatment, where low loading refers to a lesser potential for proper treatment of a subject's total tumor burden due to dose volume restrictions on INT230-6 during escalation. Cohort EC2/EC3 is defined as high loading monotherapy treatment, where high loading refers to a greater potential for proper treatment of a subject's total tumor burden due to meaningfully higher dose volume amounts allowed for INT230-6.

4.1.1. Dose Escalation

The Phase 1 portion of the study included the administration of escalating doses of INT230-6 in a 3+3+3 design for Cohorts A1, B1, EA, EC, EC2, and a 6+6 design for Cohort DEC and FEC. The SSC, comprised of the majority of study investigators plus representatives from the Sponsor, reviewed safety data regularly on an ongoing basis on all subjects. Decisions to increase the number of subjects in a cohort, to increase the concentration injected into the tumors, and the decision to begin treating deep tumors required agreement from this committee. The SSC reviewed the data on the sentinel subjects and facilitate the decision to recruit more subjects. After each escalation cohort, the SCC reviewed safety to determine escalation into the next cohort.

The following dose escalation rules applied:

- Cohorts A1, B1
 - A sentinel subject will be on treatment for 28 days
 - If there are no Dose-limiting toxicities (DLTs), upon agreement from SSC, more subjects can be enrolled
 - Cohort will continue until at least 3 subjects have completed at least 56 days (A1) or 3 doses (B1) or if 3 DLTs (A1, B1) have occurred
 - If 1 DLT is seen in the first 3 subjects, an additional 3 subjects at this dose level will be added
 - If there is one more DLT in the first 6 subjects, 3 more will be added
 - If ≥ 3 DLTs are seen in up to 9 subjects, the SCC will pause accrual and review the data
 - At the time a third DLT is observed in any dose level, even if < 9 subjects are enrolled, enrollment in that dose level will be discontinued and a lower dose level or intermediate dose level will be explored
 - A rate of DLTs that exceeds 33% is unacceptable for this population
- Cohorts EA, EC
 - No sentinel subject required
 - Cohort will continue until at least 3 subjects have completed at least 3 cycles or 3 DLTs have occurred

- If 1 DLT is seen in the first 3 subjects, an additional 3 subjects at this dose level will be added
- If there is one more DLT in the first 6 subjects, 3 more will be added
- If ≥ 3 DLTs are seen in up to 9 subjects, the SCC will pause accrual and review the data
- At the time a third DLT is observed in any dose level, even if < 9 subjects are enrolled, enrollment in that dose level will be discontinued and a lower dose level or intermediate dose level will be explored
- A rate of DLT's that exceeds 33% is unacceptable for this population
- Cohort EC2
 - No sentinel subject required
 - Cohort will continue until at least 6 subjects have completed at least 3 cycles or 4 DLTs have occurred
 - If 2 DLTs are seen in the first 6 subjects, an additional 6 subjects at this dose level will be added. If ≥ 4 DLTs are seen in up to 12 subjects, the SSC will pause accrual and review the data
 - A rate of DLT's that exceeds 33% is unacceptable for this population

Cohort DEC will include a combination of INT230-6 plus an anti-PD-1 therapy. The SCC will determine the subject population (tumor type) and the dose for this group of subjects. See Supplement A of the Protocol for details on the PD-1 agent.

4.1.2. Highest Dose

Monotherapy Cohort EC3 and Combination Cohorts DEC2 and FEC shall use up to a maximum dose of INT230-6 of 175 mL with the number of tumors being dosed per session to be decided by the investigators. The dose being set by the subject's tumor burden. After completing 5 doses of INT230-6, a maintenance single treatment of INT230-6 by intratumoral injection of up to 175 mL should be given every 9 weeks \pm 10 days into target tumors until either progressive disease, radiologic or biopsy confirmed complete response, or two years. Refer to the Study Protocol for details on combination drug dosing. Decisions to increase the number of subjects in a cohort, to change the INT230-6 dose into the tumors, and the decision as to which populations to include will require consensus from the SCC.

Up to a maximum of 44 subjects will be enrolled in Cohort DEC2. Review of DLTs will continue for Cohort DEC2 with the following conventions:

- If 2 subjects experienced a DLT, an additional 6 subjects will be entered and followed for a 28 day DLT window
- If > 3 subjects experience a DLT, the safety data will be reviewed by the SSC to determine if a lower dose or lower loading ratio per tumor of INT230-6 could be explored

- If the DLT rate is excessive during enrollment of the additional 44 subjects, the SSC reviewed the data and determine how the INT230-6 dose will be decreased, and the number of additional patients enrolled on the study at the lower dose

For Cohort FEC, up to 15 subjects could be recruited into each of the following cancer types: metastatic hepatocellular carcinoma (HCC), breast cancer (BC) and soft tissue sarcoma. The overall cohort will employ a 6 subject safety lead-in to evaluate safety and toxicities. The safety data will be reviewed by the SCC to determine whether expansion to the total of 45 subjects should be permitted. For the HCC subjects in Cohort FEC, the first accrued HCC subject shall be evaluated at Day 28. This sentinel HCC subject must receive two INT230-6 doses and 1 ipilimumab dose prior to accruing the remainder of the HCC portion of the cohort. If there are more than 2 DLTs in the HCC cohort, the SSC will evaluate de-escalation of ipilimumab.

4.1.3. Expansion Cohorts

DEC2 and FEC are expansion cohorts of 10-16 subjects with various single tumor types. These groups will allow for better point estimates of the safety and preliminary efficacy in a homogenous population of INT230-6 combined with immune checkpoint inhibitor drugs. Decisions on expansion cohorts for monotherapy (e.g., for EC3) may be made at a later time.

4.1.4. Long Term Follow up

Subjects who complete a full course of treatment including those who receive retreatment or who have discontinued treatment for any reason other than clinical or radiological progression will enter the Long Term Follow up period. During this time, subjects will be evaluated every 8 weeks for the first year and every 3 months thereafter. During this Long Term Follow up Period, if a subject progresses or receives an intervening anti-cancer therapy, the subject will then enter the Survival Follow up Period.

Subjects who discontinue treatment due to clinical or radiological progression or are Lost to Follow up or Withdraw Consent will not enter Long Term Follow up, but will enter survival follow up as outlined below.

4.1.5. Survival Follow-up Period

Following completion of the treatment and long term follow-up, as applicable, all subjects will be followed for survival. After that initial assessment of all study subjects, any surviving subjects will have their survival status assessed approximately every 3 months by either a telephone or in-person contact until study completion or termination by the Sponsor. With the exception of noting the first use of subsequent anti-cancer therapies, no other data (e.g., subsequent therapies, performance status etc.) beyond survival will be collected during these calls/visits.

4.2. Study Population

4.2.1. Selection of Study Population

Male and female subjects at least 18 years old who meet the inclusion and exclusion criteria as outlined in Protocol Section 6 will be enrolled in the study.

4.2.2. Subject Replacement

Subjects withdrawn from the study prior to completion of the DLT-evaluable period for a reason other than a DLT will be replaced.

4.3. Randomization and Blinding

This is an open-label non-randomized study.

4.4. Study Assessments

Details of scheduled assessments are presented in the study Protocol, with clarifications in Administrative letters 7 and 8. Tumor imaging occurred 12 weeks \pm 10 days after first dose and every 9 weeks \pm 10 days thereafter.

4.5. Protocol Deviations

No deviations from the protocol are anticipated. Any protocol deviations recorded will be categorized as major or minor prior to data release for the final analysis of the primary endpoint. A summary table of the major protocol deviations will be generated for both dose escalation and expansion stages. A listing of major protocol deviations will be provided, sorted by center and phase.summarized and listed.

5. SAMPLE SIZE DETERMINATION

The sample size was estimated to be between 100 and 175 subjects during dose escalation and expansion. The final enrollment consisted of 110 subjects two of whom participated in more than one cohort. Expansion cohorts may treat subjects in a specific tumor type (e.g., sarcoma that would include chordoma) to provide additional safety information and preliminary assessment of tumor response within a disease indication.

With 16 subjects treated in an expansion cohort in a given tumor type, the 90% confidence interval for an objective response rate would be 5.3% to 42% if 3 (19%) subjects had a response, 9.0% to 48% if 4 (25%) subjects had a response and 13.2% to 54.8% if 5 (31%) subjects had a response.

6. ANALYSIS POPULATIONS

6.1. All Enrolled Population

All subjects who sign the informed consent form, meet all inclusion/exclusion criteria, and are assigned to a cohort will be included. Subject disposition will be tabulated using this data set.

6.2. All Treated Population

All subjects who receive at least 1 dose or any partial dose of INT230-6. This population will be used for safety analyses and primary efficacy analyses.

6.3. Pharmacokinetic Population

All available concentration-time data from subjects who receive INT230-6 will be reported. All available derived Pharmacokinetic (PK) parameter values will be included in the PK data set and reported, but only subjects with adequate PK profiles will be included in the summary statistics and statistical analysis. Further information will be provided in the PK manual. PK sampling was eliminated in Protocol Amendment 6. Pharmacokinetic analysis will be presented separately as an addendum.

6.4. Response Evaluable Population

Response evaluable population (REP) is defined as all subjects who receive at least one dose of INT230-6, have a baseline tumor assessment with measurable disease, and one of the following: 1) at least one on-treatment tumor evaluation, 2) clinical progression, or 3) death prior to the first on-treatment tumor evaluation. This population will be used for primary efficacy analyses.

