14.2.2. All Treated Population

All subjects who receive at least 1 dose or any partial dose of INT230-6. This population will be used for safety analyses, and primary efficacy analyses.

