6.5. Scan Evaluable Population

The Scan Evaluable Population (SEP) will be defined as all subjects who receive at least one dose of INT230-6, have a baseline tumor assessment with measurable disease, and at least one on-treatment tumor evaluation via a scan at two months or later post first dose.

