7.6. Handling of Dropouts or Missing Data

Where individual data points are missing because of insufficient samples, dropouts, or other reasons, the data will be analyzed based on reduced denominators (e.g., using the response evaluable population). For survival analysis, dropouts without confirming events will be treated as censored.

All missing and partial start dates will be queried for a value. If a complete start date cannot be obtained, the following imputation rules apply in order to calculate duration of adverse event, concomitant medication use, or prior cancer history endpoints:

- Missing month and day
 - If the year of the incomplete start date is the same as the year of the date of study drug administration, then the missing month and day of the start date will be imputed to be the month and day of the start of study drug administration.
 - If the year of the incomplete start date is before the year of the date of study drug administration, December 31 will be assigned to the missing fields.
 - If the year of the incomplete start date is after the year of the date of study drug administration, January 1 will be assigned to the missing fields.

- Missing month only
 - If only the month is missing, the day will also be treated as missing, and both month and day will be replaced according to the above procedure.
- Missing day only
 - If the month and year of the incomplete start date are the same as the month and year of the date of study drug administration, the start date of study drug will be assigned to the missing field (i.e., AEs will be assumed treatment-emergent, and medications will be assumed concomitant).
 - If the month and year of the incomplete start date are before the month and year of the date of study drug administration, the last day of the month will be assigned to the missing field.
 - If the month and year of the incomplete start date are after the month and year of the date of study drug administration, the first day of the month will be assigned to the missing field.

If the stop date is complete and the imputed start date, when imputed as instructed above, is after the stop date, the start date will be imputed to equal the stop date.

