9. EFFICACY ANALYSES

Due to the method of action of the INT230-6 therapy observed over the course of the study, proper assessment utilizing RECIST or iRECIST was not possible. A response across all lesions using sum of diameters to assess efficacy over time using response criteria was not utilized. Thus, efficacy analyses will largely focus on the response of individual tumors (injected and bystander) as opposed to an overall tumor response, and any overall response will utilize the modified response criteria defined below.

Efficacy analyses will be conducted on the All Treated Population (ATP), the Response Evaluable Population (REP), and the Scan Evaluable Population (SEP). RECIST 1.1 assessments were not collected. Rather injected tumor response and non-injected tumor response utilizing some of the RECIST criteria were evaluated. Sponsor utilized RECIST principles with the injected and non-injected tumor measurements obtained. Efficacy will be determined based on a modified version of RECIST 1.1 criteria. Specifically, complete response (CR) and partial response (PR) will be defined for injected tumors followed per RECIST 1.1 utilizing target lesions. Progressive disease will be determined by clinical or radiological deterioration leading to the subject being taken off-treatment at the discretion of the investigator. Stable disease (SD) is defined as any adequate assessment not considered CR, PR, or progression. The appearance of a new lesion will not necessarily be considered progression and if possible will be assessed. Any post-baseline visit where a target lesion present at baseline was not assessed will result in a Not Evaluable (NE) assessment for that lesion. Data will be presented by treatment and, when indicated, by subgroups.

The primary efficacy parameter is the disease control rate (DCR), defined as the number of subjects obtaining a best overall response of either CR, PR, or SD as described above divided by the total number of subjects in the analysis population. The DCR will be presented with accompanying 95% exact binomial confidence intervals for each study part for the ATP population, REP, SEP, and by subgroup.

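### The SAP labels two populations as primary for efficacy where the protocol names only All Treated, and it reports disease control in three unranked sets, so the headline rate is not fixed in advance.

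*SAP*

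**What the plan says.** Protocol 14.2.2 says of the All Treated Population: "This population will be used for safety analyses, and primary efficacy analyses". Protocol 14.2.4 defines the response evaluable set and gives it no such role.

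The SAP gives the role twice. Section 6.2 says of All Treated: "This population will be used for safety analyses and primary efficacy analyses". Section 6.4 says of REP: "This population will be used for primary efficacy analyses". Besides treatment and measurable baseline disease, REP requires "one of the following: 1) at least one on-treatment tumor evaluation, 2) clinical progression, or 3) death prior to the first on-treatment tumor evaluation".

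SAP 6.5 adds SEP, which needs "at least one on-treatment tumor evaluation via a scan at two months or later post first dose" and has no alternative route for subjects who progress or die sooner. It is not called primary.

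SAP 9 divides the number of controlled subjects by a total: "divided by the total number of subjects in the analysis population". It presents the rate with "95% exact binomial confidence intervals for each study part for the ATP population, REP, SEP, and by subgroup". None of the three sets is put first. SAP 7.6, on missing data points, says that "the data will be analyzed based on reduced denominators (e.g., using the response evaluable population" as its example. SAP 13 lists no changes from the protocol's methods.

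**The concern.** SAP Table 2 makes DCR the primary endpoint for DEC2 and FEC. A primary endpoint needs one denominator, chosen before the data are examined. Here two sets carry the primary label, a third is reported beside them, and the study is open label. The SAP's revision log dates the added REP efficacy analysis and the new SEP to version 3.1 of February 2023, and the SAP already reports a final enrolment of 110. A report could therefore lead with whichever of the sets reads best and still cite the plan.

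The denominator carries unusual weight here. SAP 9 treats stable disease as any adequate assessment that is not response or progression, with no minimum duration. Progression means deterioration that takes the subject off treatment. A subject who is assessed and remains on treatment is therefore counted as controlled almost by default, so much depends on who is in the denominator without an assessment.

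**Working it through.** **1. Who is labelled primary**
- Protocol 14.2: All Treated only.
- SAP 6.2: All Treated.
- SAP 6.4: REP.
- SAP 6.5: SEP, no role stated.
- SAP 9: all three, unranked.
- SAP synopsis and Protocol 14.3.3: the DCR denominator is an efficacy population, a term that neither document defines.

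Nothing else in either document settles the choice.

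**2. Whom each step leaves out**
- All Treated to REP: subjects without measurable baseline disease, who should be few because Protocol 6.1 (criterion 7) requires it; and subjects with no on-treatment evaluation, no clinical progression and no early death. The second group are those who leave unassessed for other reasons. Protocol 12.1.5 lists adverse events, withdrawn consent and loss to follow-up among the reasons for discontinuation.
- REP to SEP: everyone without a scan at two months or later, including early clinical progressions and deaths. SAP 4.4 puts the first imaging at 12 weeks ± 10 days, that is day 84 − 10 = 74 to 84 + 10 = 94. Protocol 6.1 (criterion 14) admits subjects with a life expectancy of 8 weeks or more, or 56 days (FEC has its own criterion). Some loss before the first scheduled scan is therefore foreseeable.

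**3. The plan's own precision figures**

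SAP 5 gives 90% intervals for a response rate with n = 16. The exact Clopper-Pearson limits are Beta(0.05; x, n − x + 1) and Beta(0.95; x + 1, n − x), where the first argument is the quantile level:
- 3/16: 5.3% to 41.7% (SAP: 5.3% to 42%)
- 4/16: 9.0% to 48.4% (SAP: 9.0% to 48%)
- 5/16: 13.2% to 54.8% (SAP: 13.2% to 54.8%)

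All three reproduce after rounding.

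**4. Illustration of the denominator effect**

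The documents give no rate of unassessed subjects, so the number left out, k, is an assumption. I take n = 16, the size used in SAP 5. Let x be the number controlled in All Treated and m the number of controlled subjects among those left out. Then

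DCR in the reduced set = (x − m) / (n − k).

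With m = 0 and exact 95% intervals:

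| x | k = 0 | k = 2 | k = 4 |
|---|---|---|---|
| 8 | 8/16 = 50.0% (24.7 to 75.3) | 8/14 = 57.1% (28.9 to 82.3) | 8/12 = 66.7% (34.9 to 90.1) |
| 4 | 4/16 = 25.0% (7.3 to 52.4) | 4/14 = 28.6% (8.4 to 58.1) | 4/12 = 33.3% (9.9 to 65.1) |

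The rise is 7.1 and 16.7 points for x = 8, and 3.6 and 8.3 points for x = 4.

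The result depends on m. With x = 8 and k = 4, m = 1 gives 7/12 = 58.3% and m = 2 gives 6/12 = 50.0%, which is no rise at all. For REP, m = 0 is a reasonable approximation, because a subject never assessed cannot be classed as controlled. For SEP it need not hold: SAP 9 sets no minimum time for stable disease, so an adequate assessment before two months can make a subject controlled in All Treated while leaving that subject outside SEP.

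**The case against.** The strongest reply has three parts.

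First, the full-denominator figure cannot be hidden, because SAP 9 requires DCR with exact intervals in All Treated as well as in the other two sets. This stands, and it limits the harm to which number is called primary.

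Second, no decision rule depends on the label. There is no null rate, success threshold or test; the sizing is descriptive. In Protocol 4.2 and 4.3 safety is primary and DCR secondary, and DCR is primary for DEC2 and FEC only in SAP Table 2. This also stands, but a descriptive primary endpoint still needs one stated denominator.

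Third, SAP 9 already divides by everyone in the analysis population, and SAP 7.1 sets the same default. An unassessed subject in All Treated is thus already counted as not controlled. A reader might infer from SAP 7.6 that such subjects drop out of the All Treated rate. The text does not go that far: it concerns individual missing data points, and its example is the separately reported REP analysis. Its general wording does leave room for doubt, which one sentence would remove.

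A reader might also infer that each move to a smaller set sheds the subjects who died or deteriorated, so that REP inflates DCR in the same way as SEP. The REP definition rules this out, because it expressly keeps clinical progressions and early deaths.

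**Conclusion.** The labelling conflict is real: the SAP as written yields two primary DCRs for DEC2 and FEC, departs from the protocol's single assignment, and does not record the departure. It should be corrected.

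Its numerical size is not known. Between the two sets labelled primary, the upward effect is probably modest, since REP loses only subjects without measurable baseline disease and those unassessed for reasons other than clinical progression or early death. The larger effect belongs to SEP. The gaps of 7.1 and 16.7 points are illustrations that rest on n = 16, 8 controlled, 2 or 4 left out, and none of those left out being controlled.

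A reader might go further: with 60% control among scanned subjects and 20% to 40% of treated subjects unscanned, All Treated would show 0.60 × 0.80 = 48% down to 0.60 × 0.60 = 36%, a gap of 12 to 24 points. The documents do not support quoting that as the size of this conflict. It compares All Treated with SEP, which is not labelled primary. It assumes a loss rate that the documents do not give, and it assumes that no subject outside SEP is controlled, which SAP 9 does not guarantee.

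**What to change.** - SAP 6.4: delete the sentence that assigns primary efficacy to REP.
- SAP 6.2 and 9: state that the primary DCR uses All Treated, and that subjects without an adequate post-baseline assessment stay in the denominator as not controlled.
- SAP 6.4, 6.5 and 9: label the REP and SEP results as sensitivity analyses.
- SAP 7.6: state that reduced denominators do not apply to the primary DCR.
- SAP 13: replace the nil entry with a record that the REP and SEP efficacy analyses were added to the protocol's plan.

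The cost is wording only, with no new data and no extra tables, since all three sets are already to be reported. The headline DCR may be somewhat lower. SAP 2 requires the plan to be final before the database is locked, so the change belongs before that point.
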